10.2.2. Time to Onset of Response

- Time to onset of first response is defined as the time between the date of first IP dose and the earliest date any response (CR, PR, mCR, or HI) is first observed.
- Subjects who do not achieve any defined response during the treatment period will be censored at the date of treatment discontinuation, disease progression, or death, whichever occurs first.
- Time to onset of best response will be defined in a similar manner.
- Time to onset of first response and best response will be estimated using KM method.

10.2.3. Duration of Response

- Duration of hematologic response/improvement will be determined only for subjects who achieve a response on treatment.
- Duration of hematologic response/improvement is defined as the time from the date response/improvement is first observed until the date the subject has a subsequently documented relapse or disease progression as defined by the modified IWG 2006 criteria.
- Subjects who maintain hematologic response/improvement through the end of the treatment period will be censored at the date of treatment discontinuation or death, whichever occurs first.
- Duration of response will be assessed for both first response and best response.
- Duration of hematologic response/improvement will be estimated using KM method.

10.2.4. Progression-free Survival

- Progression-free survival (PFS), time to disease progression or death from any cause, will be calculated using date of first dose and the earliest of date of disease progression or date of death, or date of last follow-up for censored subjects.
- Time to disease progression or death from any cause is defined as the time between first dose and the earliest of disease progression or death from any cause.
- All subjects will be followed until drop-out, death, or study termination. Drop-out may be due to withdrawal of consent from further data collection or loss to follow-up. Subjects who drop-out or are alive without disease progression at study termination will have their PFS times censored at the time of last contact, as appropriate.
- The PFS will be estimated using Kaplan-Meier (KM) method.

10.2.5. Stable Disease

- A subject will be considered as having a stable disease if the disease neither responded nor progressed during or after the treatment.
- The duration of stable disease will be defined as the time between any two observations of objective disease progression (modified IWG criteria), starting from the first day of dosing with IP. Note, objective disease progression requires two observations demonstrating progressive disease, at least 8 weeks apart. The date of disease progression will be that of the earliest observation that is not followed by a discordant observation within the subsequent 8 weeks.
- Subjects who maintain stable disease through the end of the treatment period will be censored at the date of study termination.
- Duration of stable disease will be estimated using KM method.

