3.2. Secondary Endpoint(s)

The secondary endpoints of this study are:

- Overall survival;
- Time to onset of responses;
- Duration of responses;
- Progression free survival (time to disease progression or death from any cause);
- Proportion of subjects with progressive disease at baseline achieving stable disease, as well as time to achieving stable disease and duration of stable disease;
- The proportion of subjects progressing to AML and time to AML progression;
- Safety and tolerability (type, frequency, severity of AEs and relationship of AEs to CC-486 and/or durvalumab; monitoring for disease progression to AML, as well as immune- and infusion-type reactions);
- Serum/plasma PK parameters for durvalumab and CC-486, including maximum observed concentration (C_{max}), AUC, time to maximum concentration (T_{max}), terminal half-life ($t_{1/2}$), clearance (CL/F) and volume of distribution (V_z/F).

CCI

[REDACTED]

■ [REDACTED]
■ [REDACTED]

CELGENE PROPRIETARY INFORMATION

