Appendix E: Eastern Cooperative Oncology Group (ECOG) Performance Status

Eastern Cooperative Oncology Group (ECOG) Performance Status	
Grade	ECOG
0	Fully active, able to carry on all pre-disease performance without restriction.
1	Restricted in physically strenuous activity but ambulatory and able to carry out work of a light or sedentary nature, eg, light house work, office work.
2	Ambulatory and capable of all self-care but unable to carry out any work activities. Up and about more than 50% of waking hours.
3	Capable of only limited self-care, confined to bed or chair more than 50% of waking hours.
4	Completely disabled. Cannot carry on any self-care. Totally confined to bed or chair.
5	Dead.

Source: Oken MM, Creech RH, Tormey DC, Horton J, Davis TE, McFadden ET, et al. Toxicity and response criteria of the Eastern Cooperative Oncology Group. Am. J. Clin. Oncol. 1982; 5(6):649-55.

Appendix F: Hematologic Response and Improvement According to the International Working Group for MDS – modified

Hematologic Response Modified from IWG Criteria for MDS (Cheson, 2006)	
Category	Response Criteria (responses must last at least 4 weeks)
Complete Remission (CR)	Bone marrow: $\leq 5\%$ myeloblasts with normal maturation of all cell lines ^c Persistent dysplasia will be noted ^a . Peripheral blood ^c Hgb ≥ 11 g/dL Platelets $\geq 100 \times 10^9/L$ Neutrophils $\geq 1.0 \times 10^9/L^b$ Blasts 0%
Partial Remission (PR)	All CR criteria if abnormal before treatment except: – Bone marrow blasts decreased by $\geq 50\%$ over pre-treatment but still $> 5\%$ – Cellularity and morphology not relevant
Marrow CR ^b	Bone marrow: $\leq 5\%$ myeloblasts and decrease by $\geq 50\%$ over pre-treatment ^b Peripheral blood: if HI responses, they will be noted in addition to marrow CR ^b
Stable Disease (SD)	Failure to achieve any objective response (CR, PR, mCR, or HI), but no evidence of disease progression over any 8-week period
Failure	Death during treatment or disease progression characterized by worsening of cytopenias, increase in percentage of bone marrow blasts, or progression to a more advanced MDS FAB subtype than pre-treatment ^d .
Relapse After CR or PR	At least 1 of the following demonstrated by ≥ 2 values, separated by ≥ 2 weeks: – Return to pre-treatment bone marrow blast percentage – Decrement of $\geq 50\%$ from maximum remission/response levels in granulocytes or platelets – Reduction in Hgb concentration by ≥ 1.5 g/dL or transfusion dependence

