4.2.2 Secondary Endpoint(s)

The secondary endpoints of this study are:

- Overall survival;
- Time to onset of responses;
- Duration of responses;
- Progression free survival (time to disease progression or death from any cause);
- Proportion of subjects with progressive disease at baseline achieving Stable Disease, as well as time to achieving stable disease and duration of stable disease;
- The proportion of subjects progressing to AML and time to AML progression;
- Safety and tolerability (type, frequency, severity of AEs and relationship of AEs to CC-486 and/or durvalumab; monitoring for disease progression to AML, as well as immune- and infusion-type reactions);

- Serum/plasma PK parameters for durvalumab and CC-486, such as maximum observed concentration (C_{max}), area under the concentration-time curve (AUC), time to maximum concentration (T_{max}), terminal half-life ($t_{1/2}$), clearance (CL/F) and volume of distribution (V_z/F).

CCI

[REDACTED]

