10.1. Primary Efficacy Analysis

The primary assessment of efficacy will be the overall rate of response (defined as CR, PR, or mCR), and HI as determined using the modified IWG 2006 response criteria for MDS.

Hematologic response (CR, PR, mCR, and HI) will be determined by investigator assessment and responses will also be derived, summarized and analyzed separately. The percentage of these responses will be estimated separately, and the corresponding 95% confidence interval will also be provided. The percentage of subjects with other response outcomes of stable disease, failure, relapse after CR or PR, and disease progression will also be presented.

- ***Hematologic Response*** (including CR, PR, mCR, SD, Failure, Relapse after CR or PR, and Cytogenetic Response) is defined according to modified IWG 2006 criteria. Subjects will be classified according to their best response achieved during treatment for the response categories of CR, PR, mCR, SD, and failure. Only subjects who achieve CR or PR will be included in the Relapse after CR or PR category. Subjects will be evaluated for cytogenetic response regardless of their response status in other categories. Hematologic response will be presented descriptively using counts and percentages.
- ***Cytogenetic Response*** Subjects will be classified as having a complete or partial response based on the best response achieved during treatment. Responses will be presented descriptively using counts and percentages.
- The response rates at the end of Stage 2 and the associated 90% confidence interval will be estimated for each cohort which completes Stage 2. Similar estimates for Stage 1 will be provided for any cohort which does not continue to Stage 2.
- The response rates at the end of Stage 2 will be compared between cohorts of SD and PD subjects (if both cohorts finished Stage 2) using the relative risk ratio or other appropriate methods. Specifically, if relative risk method is used, the ratio of response rates for both cohorts and the associated 90% confidence interval will be estimated.

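### The stable disease rules in SAP 10.2.5 cannot be applied together: membership excludes progressors, duration needs progressions, and censoring at study termination counts largely unassessed time as stable

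*SAP*

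**What the plan says.** SAP 10.2.5 has four bullets. Protocol 10.6.2.5 has the same text, apart from a cross-reference to its Appendix F.

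- Membership: "A subject will be considered as having a stable disease if the disease neither responded nor progressed during or after the treatment".
- Duration: "The duration of stable disease will be defined as the time between any two observations of objective disease progression", counted from the first day of dosing. A note adds that progression needs two observations at least 8 weeks apart.
- Censoring: "Subjects who maintain stable disease through the end of the treatment period will be censored at the date of study termination".
- Estimation is by Kaplan-Meier.

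The endpoint served is listed in SAP 4.2.2, and likewise in Protocol 3.2: "Proportion of subjects with progressive disease at baseline achieving Stable Disease, as well as time to achieving stable disease and duration of stable disease".

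SD also appears in three other places:

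- SAP 10.1: "Subjects will be classified according to their best response achieved during treatment for the response categories of CR, PR, mCR, SD, and failure". It refers to the modified IWG 2006 criteria and sets out no SD criteria of its own.
- Protocol Appendix F: "Failure to achieve any objective response (CR, PR, mCR, or HI), but no evidence of disease progression over any 8-week period".
- SAP Appendix E: not reaching at least PR, with no progression for more than 8 weeks.

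For comparison, under SAP 10.2.3 subjects who keep a response through the end of treatment "will be censored at the date of treatment discontinuation or death, whichever occurs first".

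**The concern.** The first two bullets exclude each other. A subject who ever progresses is not SD, yet SD duration ends only at progression. The third bullet speaks of subjects who *maintain* SD, which suggests that those who later lose it were meant to be in the set. But that reading means setting the first bullet aside.

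On that wider reading the censoring date becomes the problem. Protocol Table 2 and Section 6.8.3 schedule marrow and IWG assessment only up to treatment discontinuation. The 3-monthly contacts described in SAP 4.1 then collect survival, subsequent therapies and progression to AML. Time without scheduled disease assessment would count as stable.

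Two further gaps affect the listed endpoint. The numerator changes with the section used, because SAP 10.1 and both appendices allow a subject to be SD and progress later. And time to achieving SD has no date or rule, while duration from first dose does not fit subjects who are in progression at that moment. At stake are three secondary results that two programmers could derive differently from the same data.

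**Working it through.** The documents state no SD rate or duration, so there is no plan figure to reproduce.

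**1. Literal reading.** Everyone with a progression is outside the set. Every Kaplan-Meier factor is 1 - 0/n = 1, so the curve is 100% at all times and no median is reached, whatever the data.

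**2. Definitions side by side.**

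| Source | Later progression allowed? | HI or mCR alone excluded from SD? |
|---|---|---|
| SAP 10.2.5 | No | Yes |
| SAP 10.1 | Yes (best response on treatment) | Left to the IWG criteria |
| Protocol Appendix F | Yes, after any 8-week period without progression | Yes |
| SAP Appendix E | Yes, after more than 8 weeks | No |

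The progression rows differ too. For subjects below 5% blasts, Protocol Appendix F needs a rise of at least 100% to at least 8%; SAP Appendix E needs at least 50% to above 5%. The haemoglobin falls are 1.5 and 2 g/dL.

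Illustration (assumed): if 6 of 16 subjects with PD at baseline have SD as best response, the proportion is 6/16 = 38%. If 4 of the 6 later progress, the first bullet of SAP 10.2.5 gives 2/16 = 13%.

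**3. Time credited on the wider reading.** Six cycles: 6 x 28 / 30.4167 = 5.5 months.

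- Last subject enrolled (June 2018), closure about 12 months later (SAP 4.1): 12 - 5.5 = 6.5 months.
- A subject enrolled on 7 September 2017, the date the Amendment 4 justification gives for completion of monotherapy run-in enrolment: to late June 2019 is about 21.7 months; 21.7 - 5.5 = about 16 months. No Phase 2 start date is given.

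**4. Effect on the 6-month SD rate.** Assessments follow Cycles 2, 4 and 6, at 1.8, 3.7 and 5.5 months. All counts are assumed. Each case starts from 16 subjects, one Stage 1 cohort. Those progressing at the first 8-week assessment (4, 3 and 2 subjects) are removed, since under Protocol Appendix F they were never SD. Deaths and the confirmation rule are ignored.

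| SD set | Progress at 3.7 / 5.5 | Stop at 1.8 / 3.7 / 5.5 | As written | Censored at last assessment |
|---|---|---|---|---|
| 16 - 4 = 12 | 4 / 4 | 2 / 1 / 1 | 4/12 = 33% | 6/10 x 1/5 = 12% |
| 16 - 3 = 13 | 3 / 2 | 3 / 3 / 2 | 8/13 = 62% | 7/10 x 2/4 = 35% |
| 16 - 2 = 14 | 2 / 2 | 4 / 3 / 3 | 10/14 = 71% | 8/10 x 3/5 = 48% |

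As written, everyone who stops without progression stays at risk until at least month 12, so the 6-month rate is simply the share who stop. If nobody stops, the two rules agree.

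**5. Check of direction.** A simulation of 200,000 subjects per scenario assumed exponential progression (median 3 to 12 months), independent stopping (median 3 to 9 months) and closure at 12 to 51 months. Last-assessment censoring recovered the assumed truth. Study-termination censoring overstated the 12-month rate by 16 to 44 percentage points. It did not remove progressors before 8 weeks, so it supports the direction, not the size.

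**The case against.** The best defence is that the intent is recoverable: first dose to first confirmed progression, with SD graded by the IWG criteria. The 100% curve is probably not what anyone would report. That is fair, but reaching that intent means discarding the first bullet, and the censoring rule remains wrong on the charitable reading.

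Other points stand and limit the claim:

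- Time after treatment is not wholly blind. Haematology at safety follow-up, transfusions to 90 days after the last dose, and AML progression throughout are recorded, and Protocol 6.8.7 mentions recording disease progression. Hence *largely* unassessed.
- The analysis set is mostly identifiable: the endpoint names subjects with PD at baseline, disease status is a stratum (SAP 4.1), and efficacy uses ITT. What is missing is the date SD is achieved and the time-to-SD rule.

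A reader might infer more than the documents support:

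- *About two years or more of credited time.* 24.5 months would need Phase 2 enrolment from December 2016. Protocol 4.1.2 says only that the monotherapy run-in was complete by then.
- *Censoring at the end of the Extension Phase.* SAP 4.1 puts closure at about 12 months, and Protocol Appendix J limits Extension Phase analysis to adverse events, exposure and concomitant medication.
- *The same fault in PFS.* There death is an event, and censoring at last contact is a debatable convention with a small, assumption-driven effect. It is not part of this point.

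**Conclusion.** The point holds. SAP 10.2.5 is wrong as written, not merely short of detail: it yields either no events or an inflated SD duration. It also disagrees with SAP 10.1 on whether SD survives later progression, and with both appendices on who counts as SD. Time to achieving SD is listed without an analysis.

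The contradiction rests on the text alone and is certain. The size is not. The credited time of at least 6.5 months assumes closure 12 months after the last enrolment and a stop after six cycles. The differences of 21, 27 and 23 percentage points at 6 months rest on assumed progression and stopping patterns, and vanish if nobody stops before progression.

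A reader might infer that the trial's main conclusion is exposed. It is not: these are descriptive secondary endpoints, and neither the objective response rate nor the Simon stopping decision uses them. The change should be made, but it is not critical to the design.

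**What to change.** 1. Replace the first bullet of SAP 10.2.5: SD is a best response on treatment under the Protocol Appendix F SD criterion, with later progression allowed. Align the SD and progression rows of SAP Appendix E with Protocol Appendix F.
2. For subjects with PD at baseline, assess progression from study baseline. Say openly that this departs from Appendix F, whose clinical-worsening items refer to the baseline before the injectable agent. Subjects who entered as PD on that worsening already meet them. Date SD at the first assessment completing 8 weeks without response or progression, and analyse time to achieving SD from first dose to that date.
3. Run SD duration from a stated start (first dose, or the date SD is achieved for subjects with PD at baseline) to first documented progression. State how death is handled. Censor subjects without progression at the last adequate disease assessment. Delete the wording about an interval between two progression observations.
4. State whether the requirement for two observations 8 weeks apart applies. A subject who stops at a first progression may never be confirmed. The requirement must be reconciled with Protocol Table 8 (second marrow within 4 weeks) and with assessments every 3 cycles, or 12 weeks, after Cycle 6.

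Cost: SAP wording and a matching protocol clarification, with no new data. The downside is more censoring, which may be informative if subjects stop because they are deteriorating, so estimates could still be too high. The study-termination rule can be kept as a sensitivity analysis if wanted.

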10.2.6. Disease Progression to AML

- Time to AML progression is defined as the time from the date of first dose of IP until the date the subject has documented progression to AML.
- Subjects who do not progress to AML will be censored at the date of last follow-up, the date of death, or the date of study termination.
- Time to AML progression will be estimated using KM method.

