blast percentages. Overall survival and risk of progression to AML is significantly different in the 4 risk groups. Median survival for patients in these risk groups being 5.7 years (Low), 3.5 years (INT-1), 1.2 years (INT-2), and 0.4 years (High). The median time for 25% of patients to progress to AML is 9.4, 3.3, 1.1, and 0.2 years, respectively ([Greenberg, 1997](#)).

Allogeneic bone marrow transplantation has been effective, both in patients under the age of 50 years and in those older than 50 years who are in good health and who have suitable human leukocyte antigen (HLA) matched donors. However, this approach has limited value, since most patients with MDS are older than 65 years of age and have significant comorbidities that preclude the use of this modality as it is associated with a high morbidity and mortality rate, as described in the National Comprehensive Cancer Network (NCCN) Clinical Practice Guidelines: MDS ([NCCN, 2015](#)).

For patients diagnosed with, or progressing to, higher-risk disease, the standard of care is treatment with a locally-available injectable HMA: azacitidine for injection or decitabine. Injectable HMAs can produce hematologic response or improvement in approximately half of treated patients, but responses are transient and responding disease will eventually relapse ([Grinblatt, 2008](#); [Lyons, 2009](#); [Musto, 2010](#); [Silverman, 2002](#)).

There are no approved (or proven) treatment options following failure of treatment with an injectable HMA. The mainstay of therapy in this setting among patients not eligible for autologous stem cell transplant remains supportive care, including RBC and/or platelet transfusions, treatment of infections, and the use of erythropoiesis stimulating agents (ESAs) such as epoetin alfa or darbepoetin, plus hematopoietic growth factors such as granulocyte colony-stimulating factor (G-CSF) when needed ([Lübbert, 2000](#); [NCCN, 2015](#); [Kadia, 2011](#)). Neither ESAs nor myeloid growth factors are approved for the treatment of MDS.

Thus, additional data regarding the use of potentially-effective agents in this population is greatly needed.

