6.7.2. Progression to AML

Progression to AML will be monitored as an AESI and will be included as part of the safety assessment throughout the course of the study. Progression to AML should be reported if documented at any time from signing of informed consent through death, loss to follow-up, withdrawal of consent for further data collection, or study closure, whether or not thought to be related to treatment with IP.

Events of disease progression to AML are reported in the same way as SAEs using the seriousness criterion of "important medical event" if no other seriousness criteria apply. This information must also be documented on the appropriate CRFs and in the subject's source documents. Documentation supporting the diagnosis of progression to AML (eg, confirmatory histology or cytology results, etc.) must be provided at the time of reporting as an SAE. Refer to Section 11.2 for evaluation of AEs.

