6.8.7. Survival, Progression to AML, and Subsequent MDS Therapies

All subjects discontinued from protocol-prescribed therapy for any reason should undergo treatment discontinuation procedures (Section 6.13) and be followed for survival, disease progression to AML, and subsequent MDS therapies (Section 6.14). Data regarding subsequent therapies, determination of disease progression, and date and cause of death will be recorded in the appropriate CRF.

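### Time to AML censors subjects who die without AML, so the Kaplan-Meier curve overstates AML risk whenever such a death precedes an AML event

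*SAP*

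**What the plan says.** SAP 4.2.2 lists as one secondary endpoint "The proportion of subjects progressing to AML and time to AML progression". SAP 10.2.6 starts the clock at the first dose and counts only documented AML as the event. The rule for everyone else is "Subjects who do not progress to AML will be censored at the date of last follow-up, the date of death"; study termination is the third possible censoring date. The estimator is given in one line: "Time to AML progression will be estimated using KM method". Protocol 10.6.2.6 has the same rule. Neither document mentions competing risks or cumulative incidence.

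PFS, in SAP 10.2.4, does count death; it is "defined as the time between first dose and the earliest of disease progression or death from any cause". PFS is a different endpoint and does not repair time to AML.

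Time to onset of response (SAP 10.2.2, Protocol 10.6.2.2) has a similar structure. Non-responders are censored at treatment discontinuation, progression or death, whichever comes first, and Kaplan-Meier is used.

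**The concern.** Censoring is suitable for a subject who could still have the event after leaving observation. A subject who has died without AML cannot. Kaplan-Meier nevertheless treats that subject as having the same future AML risk as those still at risk. The result could be read as AML risk in a world where nobody dies first only if AML and AML-free death were independent. That is doubtful in MDS, and without independence the curve has no clear meaning as a risk.

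Death should be common here. Protocol 1.4.1 gives median survival of 4-6 months after HMA failure in higher-risk disease. Reducing AML transformation is a stated treatment goal in the same section, so readers will look for an AML risk. They may find two: one read from the curve and one from the crude count, with no rule for reconciling them.

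**Working it through.** **The plan's own figures.** Neither document gives a sizing figure for time to AML. The only design calculation, the Simon design, reproduces (16 then 41 subjects, alpha 0.0995, power 0.801) and does not depend on this endpoint.

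**Direction.** At each AML time, with d events among n at risk, Kaplan-Meier adds S_KM × d/n to the risk, where S_KM falls only at AML events. Aalen-Johansen adds S_all × d/n, where S_all falls at AML events and at AML-free deaths. S_all is never above S_KM, so 1-KM is never below the cumulative incidence. It is strictly above once an AML-free death comes before an AML event.

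**Hand example, 16 invented subjects.** AML at months 2, 4, 7, 10; AML-free deaths at 1, 2.5, 3, 4.5, 5, 6, 8, 9; four alive and AML-free at 12. The numbers at risk at the AML times are 15, 12, 8 and 5.

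- 1-KM = 1 - (14/15)(11/12)(7/8)(4/5) = 40.1%.
- Aalen-Johansen = crude = 4/16 = 25.0%.
- With the same AML times and no deaths, all three are 25.0%.
- If the eight early exits are true losses instead of deaths, 1-KM and Aalen-Johansen are both 40.1% and crude is 25.0%. The crude figure is therefore a clean reference only with complete follow-up.

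**Size by IPSS group.** Protocol 1.1 says "The median time for 25% of patients to progress to AML is 9.4, 3.3, 1.1, and 0.2 years" for Low, INT-1, INT-2 and High. It gives median survival of 5.7, 3.5, 1.2 and 0.4 years. The formulas, with constant hazards assumed and time in months, are:

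- λ (AML) = -ln(0.75)/t25, with t25 = 112.8, 39.6, 13.2, 2.4.
- 1-KM(12) = 1 - exp(-12λ).
- Cumulative incidence(12) = λ/(λ+μ) × [1 - exp(-12(λ+μ))], where μ is the hazard of AML-free death.
- μ is solved so that overall survival is 0.5 at the stated median, with S(t) = exp(-(λ+μ)t) + λ/(λ+μ-ν) × [exp(-νt) - exp(-(λ+μ)t)] and ν = ln 2 / (median survival after AML, assumed 2-6 months). This removes deaths that follow AML.

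For INT-2, λ = 0.28768/13.2 = 0.02179, so 1-KM = 1 - exp(-0.2615) = 23.0%. Solving gives μ = 0.0312 to 0.0401 and a cumulative incidence of 19.3% to 18.5%.

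| Group | 1-KM | Cumulative incidence | Ratio |
|---|---|---|---|
| Low | 3.0% | 2.9% | 1.05 |
| INT-1 | 8.3% | 7.8-7.9% | 1.06-1.07 |
| INT-2 | 23.0% | 18.5-19.3% | 1.2 |
| High | 76% | 42-51% | 1.5-1.8 |

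Joining the INT-2 AML rate to the 4-6 month post-HMA survival gives 23.0% against 10.0-13.4% (ratio 1.7-2.3), but that mixes two populations.

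**Cohorts of 16.** These are means over 20,000 simulated cohorts at 12 months with the INT-2 AML hazard. The 5-month row is again the mixed-population case, and the loss rates are assumed.

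| AML-free death median | Loss median | 1-KM | Aalen-Johansen | Crude |
|---|---|---|---|---|
| 5 months | none | 22.9% | 11.6% | 11.6% |
| 5 months | 24 months | 22.5% | 11.6% | 10.3% |
| 14.4 months | none | 23.1% | 17.8% | 17.8% |
| 14.4 months | 24 months | 22.9% | 17.6% | 15.2% |
| no deaths | 24 months | 23.1% | 23.1% | 19.6% |

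In no simulated cohort was 1-KM below Aalen-Johansen.

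**Time to response.** The documents give no exit rates. With assumed exit medians of 3, 6 and 12 months, a true response probability of 12.5% by day 168 (six cycles) reads as 21.6%, 16.7% and 14.5% on 1-KM.

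**The case against.** Time to AML is one of several secondary endpoints, with no test, comparison or decision rule. The cohorts are small, and the Phase 2 monotherapy cohorts closed after Stage 1. An exact 95% interval for 3/16 runs from 4% to 46%, wider than any shift in the cohort simulations. The crude AML proportion is already planned, deaths are summarised separately, and the SAP never says it will present 1-KM as the probability of AML. All of this stands and limits the weight of the point. It does not remove it: any risk or median read from the curve carries the distortion, which is always upward and does not shrink with more subjects.

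The inputs are also soft. Protocol 1.1 describes general IPSS groups, while this trial enrols HMA failures and excludes rapidly progressing disease. Nor does it say whether the 25% times already allow for death. If they do, the INT-2 comparison becomes about 27-29% against 23.4-23.5%; the levels move but the ratio stays near 1.2. Simulation means are pulled up by unstable tails: with complete follow-up the median excess is 7.3 points (5-month deaths) and 4.3 points (14.4-month deaths), against means of about 11 and 5. For Low and INT-1 subjects, who are eligible, the excess is negligible. These objections affect size, not direction.

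Time to response is a weaker case. The response probability is already the primary endpoint, reported as a proportion, so a misreading is less likely. It is kept only as a secondary remark.

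**Conclusion.** The point holds. Under the stated rule, 1-KM for AML cannot fall below the cumulative incidence and exceeds it whenever an AML-free death precedes an AML event. The size depends on the risk mix, which the documents do not give. Under constant hazards and the Protocol's IPSS figures, the overstatement at 12 months is negligible in Low and INT-1 disease, about 4 points in INT-2 (23.0% against 18.5-19.3%) and 25 points or more in High (76% against 42-51%). Loss to follow-up can widen the gap to the crude proportion, so that gap is not all due to deaths. Only the description of AML risk is affected; the response rate, the stage decision and every test stand. The plan should be changed, but no trial conclusion depends on it.

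**What to change.** In SAP 10.2.6, estimate AML by the Aalen-Johansen cumulative incidence, with AML-free death as the competing event and censoring only at last follow-up or study termination. Report it beside the crude count. Align Protocol 10.6.2.6 by amendment, or record the departure in the SAP, which is lighter and enough for a descriptive endpoint. If Kaplan-Meier is kept, label the curve as not being the probability of AML.

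No new data are needed. Protocol 6.7.2 states "Progression to AML should be reported if documented at any time from signing of informed consent through death, loss to follow-up", and Protocol 6.8.7 says that "determination of disease progression, and date and cause of death will be recorded in the appropriate CRF". The cost is the wording and a change of estimator in SAS. The AML curve will read at or below the Kaplan-Meier version.

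For time to response, either describe it among responders only, or use cumulative incidence with death or treatment discontinuation without response as competing events. Do not censor at progression while a subject is still treated and assessed: Protocol 12 allows treatment to continue past progression, and Protocol 6.8.3 ends it once central pathology shows progression after at least six cycles. This would also need matching wording in Protocol 10.6.2.2 or a recorded departure.
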